#### **9.2.3.1. Infusion-Related Reaction**

As with other mAbs, infusion-related reactions may occur during or following ramucirumab and/or LY2875358 administration. Patients should be closely monitored for signs and symptoms

indicative of an infusion-related reaction, starting with the initiation of the infusion until at least 30 minutes after the infusion. Monitoring should be performed in an area where resuscitation equipment and other agents (eg, epinephrine, corticosteroids) are readily available ([Table JTBF.3](#)).

Any treatment-related infusion-related reactions are defined according to the NCI-CTCAE Version 4.03 definition (“General disorders and administration site conditions” section).

Symptoms occurring during or following infusion of investigational product may also be defined according to AE categories such as allergic reaction, anaphylaxis, or cytokine release syndrome (“Immune system disorders” section). In the setting of symptoms occurring during or following infusion of the study drugs, investigators are encouraged to use the AE term “infusion-related reaction” and any additional terms (including those not listed here) that best describe the event.

**Table JTBF.3. NCI-CTCAE Version 4 Infusion-Related Reactionsa**

Adverse Event	Grade 1	Grade 2	Grade 3	Grade 4	Grade 5
Infusion-related reaction	Mild transient reaction; infusion interruption not indicated; intervention not indicated	Therapy or infusion interruption indicated but responds promptly to symptomatic treatment (eg, antihistamines, NSAIDs, narcotics, IV fluids); prophylactic medications indicated for $\leq 24$ hours	Prolonged (eg, not rapidly responsive to symptomatic medication and/or brief interruption of infusion); recurrence of symptoms following initial improvement; hospitalization indicated for clinical sequelae	Life-threatening consequences; urgent intervention indicated	Death
Definition: A disorder characterized by adverse reaction to the infusion of pharmacological or biological substances.					
Allergic reaction	Transient flushing or rash, drug fever $<38^{\circ}\text{C} (<100.4^{\circ}\text{F})$ ; intervention not indicated	Intervention or infusion interruption indicated; responds promptly to symptomatic treatment (eg, antihistamines, NSAIDs, narcotics); prophylactic medications indicated for $\leq 24$ hours	Prolonged (eg, not rapidly responsive to symptomatic medication and/or brief interruption of infusion); recurrence of symptoms following initial improvement; hospitalization indicated for clinical sequelae (eg, renal impairment, pulmonary infiltrates)	Life-threatening consequences; urgent intervention indicated	Death
Definition: A disorder characterized by an adverse local or general response from exposure to an allergen.					
Anaphylaxis	-	-	Symptomatic bronchospasm, with or without urticaria; parenteral intervention indicated; allergy-related edema/angioedema; hypotension	Life-threatening consequences; urgent intervention indicated	Death
Definition: A disorder characterized by an acute inflammatory reaction resulting from the release of histamine and histamine-like substances from mast cells, causing a hypersensitivity immune response. Clinically, it presents with breathing difficulty, dizziness, hypotension, cyanosis, and loss of consciousness and may lead to death.					
Cytokine release syndrome	Mild reaction; infusion interruption not indicated; intervention not indicated	Therapy or infusion interruption indicated but responds promptly to symptomatic treatment (eg, antihistamines, NSAIDs, narcotics, IV fluids); prophylactic medications indicated for $\leq 24$ hours	Prolonged (eg, not rapidly responsive to symptomatic medication and/or brief interruption of infusion); recurrence of symptoms following initial improvement; hospitalization indicated for clinical sequelae (eg, renal impairment, pulmonary infiltrates)	Life-threatening consequences; pressor or ventilator support indicated	Death

Definition: A disorder characterized by nausea, headache, tachycardia, hypotension, rash, and shortness of breath; it is caused by the release of cytokines from the cells.

Abbreviations: IV = intravenous; NCI-CTCAE = National Cancer Institute Common Terminology Criteria for Adverse Events, version 4.03; NSAID = nonsteroidal anti-inflammatory drug.

a Premedication must be provided in the setting of a prior Grade 1-2 infusion-related reaction.

Consistent with usual medical practice, selected parenteral medications may be utilized for Grade 2 allergic/hypersensitivity reaction as detailed below. The sponsor physician or designee should be contacted immediately if questions arise concerning the grade of the reaction. The following are treatment guidelines for infusion-related reactions:

#### Grade 1

- Slow the infusion rate by 50% for the duration of the infusion and all subsequent infusions.
- Monitor the patient for worsening of condition.
- For subsequent infusions, premedicate with diphenhydramine hydrochloride 50 mg IV (or equivalent); additional premedication may be administered at the investigator's discretion.

#### Grade 2

- Stop the infusion.
- Administer diphenhydramine hydrochloride 50 mg IV (or equivalent), acetaminophen 650 mg orally for fever, and oxygen.
- Resume the infusion at 50% of the prior rate for the duration of the infusion and all subsequent infusions once the infusion-related reaction has resolved or decreased to Grade 1; the infusion duration should not exceed 2 hours for each of the study drugs
- Monitor for worsening of condition.
- For subsequent infusions, premedicate with diphenhydramine hydrochloride 50 mg IV (or equivalent); additional premedication may be administered at the investigator's discretion.
- For a second Grade 1 or 2 infusion-related reaction, administer dexamethasone 8-10 mg IV (or equivalent); then, for subsequent infusions, premedicate with diphenhydramine hydrochloride 50 mg IV (or equivalent), acetaminophen 650 mg orally, and dexamethasone 8-10 mg IV (or equivalent).

#### Grade 3

- Stop the infusion and disconnect the infusion tubing from the patient.
- Administer diphenhydramine hydrochloride 50 mg IV (or equivalent), dexamethasone 8-10 mg IV (or equivalent), bronchodilators for bronchospasm, and other medications/treatment as medically indicated.
- Patients who have a Grade 3 infusion-related reaction will not receive further investigational product causing this infusion-related reaction.

#### Grade 4

- Stop the infusion and disconnect the infusion tubing from the patient.
- Administer diphenhydramine hydrochloride 50 mg IV (or equivalent), dexamethasone 8-10 mg IV (or equivalent), and other medications/treatment as medically indicated.
- Give epinephrine or bronchodilators as indicated.
- Hospital admission for observation may be indicated.

- Patients who have a Grade 4 infusion-related reaction will not receive further investigational product causing this infusion-related reaction.

If a patient should have an infusion-related reaction to the study drugs, all attempts should be made to obtain blood samples for both immunogenicity and PK analysis as close to the onset of the event as possible, at the resolution of the event, and 30 days following the event.

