### **9.2.1. Ramucirumab Dosing Schedule**

Ramucirumab will be dosed at 8 mg/kg and administered as a 1-hour IV infusion prior to the administration of LY2875358 on Days 1 and 15 of a 28-day cycle in Part A and B of this study. The infusion rate of ramucirumab should not exceed 25 mg/min.

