### **9.2.2. LY2875358 Dosing Schedule**

LY2875358 will be administered after a minimum of a 60-minute observation period (minimum of 30-minute observation period in Cycle 2 and beyond) following the end of the ramucirumab infusion on Days 1 and 15 of a 28-day cycle. LY2875358 will be administered as an IV infusion using either a central or a peripheral venous line. No in-line, sterile, nonpyrogenic filter should be used. To ensure that the total dose of LY2875358 will be administered, the line should be flushed at the end of the infusion (see pharmacy instructions). The LY2875358 infusion, including the flushing of the line, should be administered over a period of approximately 90 minutes. If it is determined that a reduced LY2875358 infusion time is safe and feasible, the investigators will be notified in writing and the pharmacy instructions will be updated to reflect the change.

No premedication is recommended prior to infusion of LY2875358. Premedication may be provided at the investigator's discretion. Premedication must be provided in the setting of a prior Grade 1-2 infusion-related reaction, as detailed in Section 9.2.3.1. All premedication administered must be adequately documented on the eCRF.

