#### **9.2.2.1. Dose Escalation of LY2875358 in Part A**

In Part A, dose levels of LY2875358 previously tolerated as monotherapy and in combination with erlotinib in Study JTBA will be administered following the proposed dose escalation scheme below:

**Dose level 1:** LY2875358 750-mg flat dose as a 90-minute IV infusion after a minimum of a 60-minute observation period (minimum of 30-minute observation period in Cycle 2 and beyond) following the end of the ramucirumab 8-mg/kg infusion on Days 1 and 15 of a 28-day cycle

**Dose level 2:** LY2875358 2000-mg flat dose as a 90-minute IV infusion after a minimum of a 60-minute observation period (minimum of 30-minute observation period in Cycle 2 and beyond) following the end of the ramucirumab 8-mg/kg infusion on Days 1 and 15 of a 28-day cycle

Dose escalation will be guided primarily by safety assessments, in particular AEs, during Cycle 1. By nature of being a dose escalation study, data will be evaluated on an ongoing basis to determine a recommended schedule and dose range of LY2875358 that may be safely administered in combination with ramucirumab on Days 1 and 15 of a 28-day cycle.

The sponsor and investigators will review and discuss all patient safety data prior to dose escalation. In addition, if available at the time of dose escalation decision, PK results will be used as secondary/supporting data for dose escalation. Intermediate dose levels for LY2875358 (or a dose below the starting dose) may be considered based on appearance of toxicity or PK/PD modeling, if deemed appropriate by agreement between the investigators and the sponsor. If during the dose escalation, a new sequence of drug administration (eg, inverse order of administration or sequential dosing of the study drugs on separate days) should be indicated for safety or PK reasons, or preclinical data suggest that this may pose a better regimen, then the investigators together with the sponsor will decide on this change and inform the ERBs in writing. No protocol amendment will be required.

No dose escalation can occur without prior discussion and agreement between the investigator and the Lilly CRP/CRS; the decision will be documented in writing. Based on the ongoing safety reviews, modifications to the dose escalation strategy or other design elements may be made via protocol amendment to ensure patient safety. Intrapatient dose escalation will not be permitted in this study.

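### After a first Grade 2 reaction to LY2875358, the half rate ordered for later infusions needs about 3 hours, but the same bullet caps each infusion at 2 hours

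*Protocol*

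**What the plan says.** The treatment guidelines in Protocol Section 9.2.3.1 follow Table JTBF.3 and are arranged by grade.

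- **Grade 1:** "Slow the infusion rate by 50% for the duration of the infusion and all subsequent infusions". No limit on duration is given.
- **Grade 2:** the infusion is stopped, and diphenhydramine, acetaminophen for fever, and oxygen are given. Once the reaction has resolved or fallen to Grade 1, the order is "Resume the infusion at 50% of the prior rate for the duration of the infusion and all subsequent infusions". After a semicolon, the same bullet says that "the infusion duration should not exceed 2 hours for each of the study drugs".
- **Second Grade 1 or 2 reaction:** dexamethasone is given, and later infusions are premedicated with diphenhydramine, acetaminophen and dexamethasone. This bullet does not mention the rate.

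The standard times are set elsewhere. Ramucirumab is "administered as a 1-hour IV infusion" (Section 9.2.1). The LY2875358 infusion, flush included, "should be administered over a period of approximately 90 minutes" (Section 9.2.2). Both planned dose levels carry that time, for example "LY2875358 2000-mg flat dose as a 90-minute IV infusion" (Section 9.2.2.1), and SAP Section 5.1 repeats 90 minutes.

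Three further provisions bear on the point:

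- Section 9.2.2 leaves room for a shorter LY2875358 infusion by written notice, in the clause that begins "If it is determined that a reduced LY2875358 infusion time is safe and feasible". No shorter time is given.
- Section 9.2.2 has the line flushed so that the whole dose is delivered, and Section 9.2.3.3 rules out changing the LY2875358 dose within a patient.
- Section 9.1.2 gives 6 hours at room temperature for the reconstituted LY2875358 product and refers to the pharmacy binder for anything further.

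**The concern.** The bullet fixes a rate and a maximum time for the same infusion. With the dose also fixed, the rate determines the time, so the two can agree only if the standard infusion is short enough. Two hours is exactly twice the ramucirumab time, yet the bullet applies it to both drugs.

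What is at stake is the handling of patients who have already reacted to LY2875358. A site must either overrun the cap or run faster than ordered, and different sites may choose differently. If a site lets the cap override, a Grade 2 patient receives later LY2875358 infusions faster than a Grade 1 patient, whose 50% slowing has no cap.

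**Working it through.** **Inputs**

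- Standard ramucirumab time: 60 minutes (Protocol Section 9.2.1)
- Standard LY2875358 time: about 90 minutes, flush included (Sections 9.2.2 and 9.2.2.1)
- Rate after a Grade 2 reaction: 50% of the prior rate; for a first reaction the prior rate is the standard rate (Section 9.2.3.1)
- Cap: 120 minutes for each drug (Section 9.2.3.1)

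**Step 1. Duration of a later full infusion.** With dose and volume fixed and a constant rate, duration = standard time / 0.5.

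| Drug | Calculation | Result | Cap |
|---|---|---|---|
| Ramucirumab | 60/0.5 | 120 min | met exactly |
| LY2875358 | 90/0.5 | 180 min | exceeded by 60 min |

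The plan's 2-hour figure is therefore reproduced for ramucirumab and not for LY2875358.

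**Step 2. What it takes to meet the cap with LY2875358.**

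- Rate needed: 90/120 = 75% of standard, which is 0.75/0.50 = 1.5 times the ordered rate.
- Stopping at 120 minutes at half rate: 0.5 × 120/90 = 67% of the dose delivered, so a third is not given.
- Longest standard time that fits at half rate: 120 × 0.5 = 60 minutes.

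**Step 3. Rates in mg/min.**

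| Dose | Standard (90 min) | Half rate (180 min) | Needed for cap (120 min) |
|---|---|---|---|
| 2000 mg | 2000/90 = 22.2 | 2000/180 = 11.1 | 2000/120 = 16.7 |
| 750 mg | 750/90 = 8.3 | 750/180 = 4.2 | 750/120 = 6.3 |

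These are approximate, because the 90 minutes includes the flush.

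**Step 4. Does the flush rescue it?** The documents give no flush time. Assume f of the 90 minutes is flush and is not slowed. The total is then 2 × (90 − f) + f = 180 − f. For f from 5 to 30 minutes this gives 175 to 150 minutes, still over 120.

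**Step 5. The infusion in which the reaction occurs.** If the reaction starts at minute t, running time is t + 2 × (90 − t) = 180 − t. This fits 120 minutes only if t is 60 or more. The general conflict therefore concerns the later, full infusions.

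**The case against.** The strongest reply is that these are guidelines, that the cap is worded as a recommendation, and that it follows a semicolon in the same bullet. It can then be read as limiting the rate order: slow to half, but not beyond 2 hours. That is a possible intention. It still means running LY2875358 at 75% or more where the text orders 50%, and nothing says that the cap governs.

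Several other points stand and narrow the concern.

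- The faster rate for Grade 2 than for Grade 1 arises only if a site lets the cap override. Rate is also not the whole of management: Grade 2 care stops the infusion, gives medication and resumes only after improvement.
- The documents do not say why the cap is 2 hours. If stability or handling lies behind it, a 3-hour infusion may not be acceptable. The pharmacy instructions would settle this, and they are not part of the two documents.
- The documents give no frequency of Grade 2 reactions to LY2875358. Protocol Section 9.2.2.2 does not count infusion reactions as DLTs by default.
- The sponsor may shorten the standard infusion. At 60 minutes or less the conflict would disappear, but neither document sets such a time.

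A reader might also infer that a second reaction halves the rate again, giving 60/0.25 = 240 minutes for ramucirumab and 90/0.25 = 360 minutes for LY2875358, so that the cap fails for both drugs. The documents do not establish this. The bullet for a second Grade 1 or 2 reaction adds medication and orders no further rate cut. Those figures come from carrying the words about the prior rate over to a repeat event, and they are not part of the finding.

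**Conclusion.** Wrong as written, for LY2875358 only. After a first Grade 2 reaction, the ordered rate gives about 180 minutes for each later full infusion against a limit of 120 in the same bullet. The dose cannot be cut to fit, and no text ranks the two instructions. Ramucirumab meets the limit exactly, without margin.

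This rests on the standard time of about 90 minutes, a constant rate, delivery of the full dose, and duration counted as running time. A reader might infer that patients will in fact be infused too fast, or that the trial's results are at risk. The documents support neither: they do not say which instruction sites will follow or how rate affects recurrence, and ORR, power and error rates do not depend on this bullet. It is a minor operational safety correction.

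**What to change.** In the Grade 2 bullet of Protocol Section 9.2.3.1:

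1. Make the cap drug-specific: 2 hours for ramucirumab and about 3 hours for LY2875358, both at the 50% rate. The 3 hours depends on the sponsor confirming in-use stability of the prepared infusion against the pharmacy instructions. The 6 hours in Section 9.1.2 covers the reconstituted product only.
2. If stability does not allow 3 hours, state for LY2875358 the reduced rate that fits the cap: about 75% of standard for 2 hours.
3. Add that after a repeat Grade 1 or 2 reaction the rate stays at 50% of standard, with the premedication already listed for a second reaction. Under item 1, both drugs then remain within their caps.

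The cost is one bullet, the matching pharmacy instruction and a stability check. At each affected visit, LY2875358 would take 180 − 120 = 60 minutes more than the current limit, or 180 − 90 = 90 minutes more than an infusion without a reaction. From Cycle 2, with ramucirumab at its standard rate, the minimum time from the start of ramucirumab to the end of LY2875358 is 60 + 30 + 90 = 180 minutes without a reaction. It would be 60 + 30 + 180 = 270 minutes under item 1. Sample size and analysis do not change.

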### **9.2.3.2. Treatment Guidelines and Dose Modifications for Ramucirumab-specific Adverse Events**

Dose modifications of ramucirumab are permitted in the setting of non-life-threatening, reversible Grade 3-4 clinical AEs (eg, fever) considered to be at least possibly related to ramucirumab.

- For toxicities that resolve to Grade  $\leq 1$  or baseline, ramucirumab may be re-administered at a dose of 8 mg/kg
- If a second instance of such an event occurs, ramucirumab should be subsequently re-administered at a dose of 6 mg/kg Q2W.
- A second dose reduction to 5 mg/kg Q2W is permitted for this level of event (Grade 3-4).

Any further dose reduction of ramucirumab below 5 mg/kg is not permitted, and if the criteria for a ramucirumab dose reduction are met for patients at 5 mg/kg ramucirumab Q2W, ramucirumab must be discontinued. If the dose of ramucirumab is reduced, subsequent dose increases are not permitted. If a patient's dose is reduced or treatment is discontinued as a result of an AE, study site personnel must clearly report the circumstances and data leading to any such dosage reduction or discontinuation of treatment.

Patients who enter the study with symptoms or laboratory values equivalent to NCI-CTCAE Version 4.03 Grade 1-2 AEs should not have dose reductions related to the persistence or mild worsening of those symptoms or laboratory values; dose reductions may be warranted if worsening of symptoms or laboratory values is clinically significant in the opinion of the investigator. Asymptomatic Grade 3-4 laboratory abnormalities should not result in dose interruptions, modifications, or discontinuation of study therapy unless determined to be clinically significant by the investigator (or unless otherwise specified in the study protocol).

#### **9.2.3.2.1. Hypertension**

The following are treatment guidelines for hypertension that develops during the study.

##### Grade $\leq 3$

- If the hypertension is not associated with symptoms, continue ramucirumab and initiate antihypertensive therapy.
- If the hypertension is associated with symptoms, hold ramucirumab until symptoms resolve and initiate antihypertensive therapy.
- If ramucirumab is held more than once for hypertension (ie, symptomatic hypertension, markedly elevated BP unresponsive to antihypertensive therapy), the dose of investigational product should be reduced upon re-treatment to 6 mg/kg Q2W. A second

dose reduction to 5 mg/kg Q2W should be undertaken if an additional postponement of ramucirumab is required.

Grade 3 (systolic BP  $\geq 160$  mmHg or diastolic BP  $\geq 100$  mmHg; medical intervention indicated; more than 1 drug or more intensive therapy than previously used indicated)

- For Grade 3 hypertension not associated with symptoms, continue ramucirumab with more intensive antihypertensive therapy. If systolic BP remains  $\geq 160$  mmHg or diastolic BP remains  $\geq 100$  mmHg  $>3$  weeks after initiation of additional antihypertensive therapy, hold ramucirumab while continuing appropriate antihypertensive therapy.
- If the hypertension is associated with symptoms, hold ramucirumab while continuing appropriate antihypertensive therapy.
- If ramucirumab is held more than once for hypertension (ie, symptomatic hypertension, markedly elevated BP unresponsive to antihypertensive therapy), the dose of ramucirumab should be reduced upon re-treatment to 6 mg/kg Q2W. A second dose reduction to 5 mg/kg Q2W should be undertaken if an additional postponement of investigational product is required.

Grade 4 or refractory

- Patients with Grade 4 hypertension (life-threatening consequences, eg, malignant hypertension, transient or permanent neurologic deficit, hypertensive crisis, or urgent intervention indicated) or patients whose hypertension is poorly controlled ( $>160$  mmHg systolic BP or  $>100$  mmHg diastolic BP for  $>4$  weeks) despite appropriate oral medication ( $>2$  oral agents at MTD) will be discontinued from ramucirumab.

#### **9.2.3.2.2. Proteinuria**

If, while receiving ramucirumab, a patient has proteinuria  $\geq 2+$  per a dipstick or routine urinalysis test, ramucirumab will continue as scheduled, and a 24-hour urine collection will be conducted prior to the subsequent scheduled treatment cycle. If the protein level is  $<2$  g/24 hours, the patient will continue on ramucirumab at the same dose without interruption. If the protein level is 2 to 3 g/24 hours, ramucirumab for the subsequent cycle will be held for 2 weeks and a 24-hour urine collection will be repeated. Treatment with ramucirumab will resume at a reduced dose level (6 mg/kg Q2W) once the protein level returns to  $<2$  g/24 hours. A second dose reduction of ramucirumab to 5 mg/kg every 2 weeks is permitted if proteinuria  $>2$  g/24 hours recurs. Ramucirumab will be discontinued if the protein level is  $>3$  g/24 hours, if there is a third occurrence of proteinuria  $>2$  g/24 hours, or if the protein level does not return to  $<2$  g/24 hours within 2 weeks.

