## **8.2. Discontinuations**

### **8.2.1. Discontinuation of Patients**

The criteria for enrollment must be followed explicitly. If the investigator site identifies a patient who did not meet enrollment criteria and who was inadvertently enrolled, the sponsor must be notified. If the sponsor identifies a patient who did not meet enrollment criteria and who was inadvertently enrolled, the investigator site will be notified. A discussion must occur between the sponsor CRP/clinical research scientist (CRS) and the investigator to determine whether the patient may continue in the study, with or without investigational product. Inadvertently enrolled patients may be maintained in the study and on investigational product when the Lilly CRP/CRS agrees with the investigator that it is medically appropriate for that patient. The patient may not continue in the study with or without investigational product if the Lilly CRP/CRS does not agree with the investigator’s determination that it is medically appropriate for the patient to continue. The investigator must obtain documented approval from the Lilly CRP/CRS to allow the inadvertently enrolled patient to continue in the study with or without investigational product.

Patients will be discontinued from the study drug(s) in the following circumstances:

- The patient has evidence of progressive disease.
  - NOTE: In select cases, after discussion with the sponsor, treatment beyond progression may be permissible if the patient is thought to be deriving ongoing benefit from the study therapy. For instance, local therapies, such as radiation treatment to control isolated areas of CNS progression, may be permissible provided study drugs are held on the days of local therapy. Additional systemic therapy, however, is not allowed. This option is contingent upon study drug

availability. Patients may continue until they fulfill another one of the criteria for study discontinuation.

- The patient experiences unacceptable toxicity that is deemed related to study drug(s) (eg, a persistent moderate toxicity that is intolerable to the patient).
- The patient experiences a Grade 3 or 4 infusion-related reaction related to study drug(s). The patient should be permanently discontinued from ramucirumab for any of the following events (see Section 9.2.3.2):
  - Grade 4 hypertension or persistent/recurrent hypertension
  - Grade 4 proteinuria or persistent/recurrent proteinuria  $>3$  g/24 hours
  - Grade 3 or 4 ATE

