Radiological Tumor Assessment g	X										Every 6 weeks after initiation of study treatment; after Cycle 9 every 2-4 cycles as clinically indicated	
Functional Tumor Imaging	X h										FDG-PET mandatory in Part B1 (gastric) 6 weeks after initiation of study therapy	

Abbreviations: CNS = central nervous system; CT = computed tomography; CTCAE = Common Terminology Criteria for Adverse Events; DCE-MRI = dynamic contrasted-enhanced magnetic resonance imaging; ECG = electrocardiogram; ECOG = Eastern Cooperative Oncology Group; FDG-PET = 2-deoxy-2[F-18]fluoro-D-glucose positron emission tomography; FLT-PET = 3-deoxy-3[F-18]fluorothymidine positron emission tomography; fT4 = free thyroxine; PD = pharmacodynamics; PET = positron emission tomography; PK = pharmacokinetics; TSH = thyroid-stimulating hormone; V = visit.

a Short-term follow-up begins on the day after the patient's last dose of study drug and ends approximately 30 days later. This visit should be scheduled  $30 \pm 3$  days after last dose of study drug.

b Electrocardiograms must be recorded before any study drug is administered. In Cycle 1, Day 1 and 15 only, additional ECGs must be recorded pre- and post-LY2875358 infusion, immediately before collecting the corresponding PK samples.

- c Local hematology, coagulation tests, and urinalysis may be done within 2 days prior to administration of study drugs (except Cycle 1, Day 1 [within 3 days]). An additional local chemistry panel according to local standard of care may be done and used for on-study dosing decisions; if done so, chemistry testing must also still be performed by the central laboratory at the regularly scheduled time points. The central chemistry laboratory results will be used for patient eligibility and subsequent safety analyses. In exceptional cases, patient may be enrolled based on local chemistry results after discussion with the sponsor if central laboratory samples results required for eligibility are not available in a timely manner (e.g., due to inclement weather conditions).
- d If, while receiving the investigational product(s), a patient has proteinuria  $\geq 2+$  per a dipstick or routine urinalysis test, a 24-hour urine collection will be conducted prior to the subsequent scheduled treatment (see Section 9.2.3.2.2).
- e Samples will be collected at Cycle 3, Cycle 5, Cycle 7, Cycle 9, and every 4 cycles thereafter while patient is on study treatment.

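### A first, single 24-hour urine protein above 3 g that is not Grade 4 meets the ramucirumab stopping criterion in Protocol Section 9.2.3.2.2 but not the one in Section 8.2.1

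*Protocol*

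**What the plan says.** Three places in the current protocol govern proteinuria during ramucirumab treatment.

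- **Section 9.2.3.2.2** opens its stopping sentence with "Ramucirumab will be discontinued if the protein level is $>3$ g/24 hours". The same sentence gives two further triggers: "if there is a third occurrence of proteinuria" above 2 g/24 h, and failure to fall back below 2 g/24 h in 2 weeks. The preceding step reads "If the protein level is 2 to 3 g/24 hours, ramucirumab for the subsequent cycle will be held for 2 weeks", with a repeat collection. For dipstick proteinuria of 2+ or more, the section places the 24-hour collection before the next treatment cycle.
- **Section 8.2.1**, in its list of events for permanent discontinuation of ramucirumab, has "Grade 4 proteinuria or persistent/recurrent proteinuria" above 3 g/24 h. The list cross-refers to Section 9.2.3.2.
- **Attachment 1, footnote d** has the same dipstick trigger but says that "a 24-hour urine collection will be conducted prior to the subsequent scheduled treatment". It cross-refers to Section 9.2.3.2.2.

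The SAP restates no proteinuria rule. Its Section 5.1 points to Protocol Section 8.2.1 for the discontinuation criteria.

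**The concern.** The same threshold, 3 g/24 h, appears in two stopping rules. One attaches no condition to it. The other requires persistence or recurrence, with Grade 4 as a separate trigger. A site working from the adverse event guidance and a site working from the discontinuation list could reach different decisions about the same laboratory result.

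The primary objective concerns safe administration of the combination. Discontinuations by reason (SAP Section 6.7), dose delays and adjustments (Section 6.11) and dose reductions (Section 6.11.1) are all planned outputs. If the rule applied varies between sites, those outputs partly reflect which page was read, in cohorts of about 15 patients. The time at which the quantitative urine result becomes available also differs between the text and the schedule.

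**Working it through.** The plan gives no figure here to reproduce, and no sample size or error-rate calculation applies. The check is to put the same findings through both texts.

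| 24-hour urine protein finding | Section 9.2.3.2.2 | Section 8.2.1, proteinuria item |
|---|---|---|
| First value of 2 to 3 g | Hold and repeat | Not listed |
| First, single value above 3 g, not Grade 4 | Discontinue | Criterion not met |
| Persistent or recurrent value above 3 g | Discontinue (already triggered by the first value) | Discontinue |
| Grade 4 | No trigger by grade; acts on g/24 h | Discontinue |
| Above 2 g for the third time | Discontinue | Not named |
| Not back below 2 g in 2 weeks | Discontinue | Not named |

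The second row is the contradiction. Four observations bear on it.

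1. In Section 9.2.3.2.2 the absence of a condition on the 3 g clause does not look accidental. The same sentence counts occurrences for the 2 g threshold and sets a time limit for recovery. One result above 3 g is enough.
2. The hold-and-repeat band ends at 3 g. Section 9.2.3.2.2 offers nothing for a first value above 3 g except discontinuation, so it has no step in which persistence could be established.
3. If Section 9.2.3.2.2 governs, the persistence or recurrence condition in Section 8.2.1 has almost nothing left to act on, because the patient is off ramucirumab after the first value. If Section 8.2.1 governs, the unconditional clause in Section 9.2.3.2.2 does not hold as written.
4. The documents define neither persistent/recurrent nor Grade 4 proteinuria, so the gap cannot be closed from the text.

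**Collection time (secondary).** Doses fall on Days 1 and 15 of a 28-day cycle (Section 9.2.1), so the next cycle starts on Day 29.

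- Finding on Day 1 or Day 8: footnote d requires collection before Day 15; Section 9.2.3.2.2 requires it before Day 29. The difference is 29 − 15 = 14 days, with one further scheduled ramucirumab dose in between.
- Finding on Day 15 or Day 22: the next treatment is Day 1 of the next cycle, and the two texts coincide.

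**Where the criterion does not reach.** The DLT definition (Protocol Section 9.2.2.2) rests on Cycle 1 grades and on joint investigator and sponsor judgement, and does not cite the proteinuria stopping rule. ORR takes all treated patients as its denominator (SAP Section 6.12). The sample size and the two-stage design parameters do not use the criterion.

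**The case against.** The strongest reply is that the documents already link the passages. The Section 8.2.1 list points to Section 9.2.3.2, and footnote d points to Section 9.2.3.2.2. Section 8.2.1 does not claim to be exhaustive and never says that a patient with one value above 3 g/24 h continues. A site that follows Section 9.2.3.2.2 breaches neither text. The general rule in Section 9.2.3.2, "Asymptomatic Grade 3-4 laboratory abnormalities should not result in dose interruptions, modifications, or discontinuation of study therapy", yields where the protocol specifies otherwise.

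Part of this stands. It explains the last two rows of the table: a short list may leave out triggers that the detailed section supplies. It does not explain the second row, because there Section 8.2.1 names the same threshold and attaches a condition to it. A cross-reference is not an order of precedence, and the exception to the general rule does not help when the protocol specifies two different things.

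On collection time the reply is stronger. Any collection before the next treatment is also before the next cycle, so the two texts can both be met. Section 9.2.3.2.2 may also use the word cycle loosely, since it holds ramucirumab for the subsequent cycle for only 2 weeks of a 28-day cycle. This is an imprecision to tidy, secondary to the stopping rule.

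A reader might also infer a size from the 5.1% rate of Grade 3 or higher proteinuria in the cited renal cell study (Protocol Section 5.2.1.3): 0.051 × 15 = 0.8 patients per cohort, or 0.051 × 45 = 2.3 in an expanded one. The documents do not support that. The rate is about 2 events in 39 patients (0.051 × 39 = 2.0) on monotherapy in one tumor type. The Grade 3 or higher events named for the hepatocellular study and for the lung study with docetaxel do not include proteinuria. The documents do not equate Grade 3 with more than 3 g/24 h. They also give no share of events that are single and transient, which are the only ones on which the two rules disagree. Expansion to 45 is optional.

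**Conclusion.** The contradiction is real and lies in current protocol text. For a first, single value above 3 g/24 h that is not Grade 4, the two sections give different results, and nothing in the protocol ranks them. It should be corrected, because it concerns a safety stopping rule and is more than a clerical slip.

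Its reach is limited. Sites could act differently; the documents do not show that they would. What is exposed is consistent safety conduct and the descriptive summaries of discontinuations and dose adjustments. The number of patients affected cannot be derived from the documents and may be zero in a given cohort. A reader might go further and infer that the tolerability conclusion turns on this point. That is not supported: DLTs and ORR do not use the criterion, the summaries are descriptive, and Section 8.2.1 allows LY2875358 to continue, after discussion with the sponsor, when ramucirumab alone is stopped.

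The conclusion assumes only that the 3 g clause in Section 9.2.3.2.2 means what it says, without an unstated requirement for repetition. The collection-time difference is real for findings before Day 15 and is secondary.

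**What to change.** Reconcile Protocol Section 8.2.1, Section 9.2.3.2.2 and Attachment 1 footnote d so that one proteinuria stopping criterion and one time for the 24-hour collection apply throughout. Any term kept in the final rule that the documents leave undefined, such as persistent/recurrent or Grade 4 proteinuria, needs a definition. Section 8.2.1 should either carry all the proteinuria triggers or state that Section 9.2.3.2.2 contains the full rule. Which criterion and which time apply is a clinical decision for the sponsor and investigators, and none is proposed here.

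The cost is protocol wording. Sample size, analysis methods and the SAP's planned outputs are unaffected. Amendment (b) already lists a change to Section 9.2.3 made to bring it into line with the discontinuation criteria, so this would extend the same exercise to proteinuria.
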